**Randomized Evaluation of Voucher Interventions for
Value and Effectiveness (REVIVE) in Philippines**

**Study protocol
February 2026**

1. Background

The Department of Social Welfare and Development (DSWD) in Philippines is committed to addressing hunger, food insecurity, and malnutrition through evidence-based social protection programs. Technical Assistance (TA) project of the Asian Development Bank (ADB)- TA 10206 has provided rapid and on-demand support to the DSWD since December 2023 to address these challenges, including through pilot studies, REFUEL project preparation and due diligence, capacity building, and impact evaluations. The TA will also support diagnostics and analysis for the REVIVE pilot.

The REVIVE is a pilot and special study intended to test the impact of different voucher amounts together with enhancements in SBCC on household food security, hunger, and nutrition. From December 2023 – July 2024, a pilot supported under TA 10206 was implemented providing a 3,000-peso voucher together with monthly nutrition-sensitive social and behavior change communication (SBCC) sessions on similar household and child level outcomes. Vouchers were structured such that 50% could be utilized for carbohydrates and oils, 30% for proteins, and 20% for fruits and vegetables. Despite positive impacts from a rigorous evaluation, the results indicated that impacts could be enhanced with certain design modifications and further testing.

For example, the net value of food acquired by the household responded strongly for proteins, fruits and vegetables, but weakly for carbohydrates and oils, which were already being consumed at nearly recommended levels. While there was a statistically significant reduction in reported hunger and food insecurity, the magnitude of reductions was relatively small, particularly given the average household size of 7, which reduced the per capita value of vouchers. Subsequent calculations showed that the gap in food expenditure between the cost of a healthy diet and expenditures of households in the bottom income decile is much more than the 3,000-peso voucher amount. Analysis revealed that the gap is between 5000 and 8000 pesos monthly per household.

Results and recommendations from the first pilot offered several important lessons and recommendations which have informed the design of REVIVE including the need to: i) restructure the voucher allocations to 10% for carbohydrates and oils, 45% for proteins, and 45% for fruits and vegetables; ii) allow continuous redemptions, rather than monthly ones, given a lack of refrigeration among beneficiaries and inability to store perishable products; iii) pilot test voucher amounts of 5000 or 8000 pesos per household per month; and iv) enhance the SBCC to improve nutrition knowledge effects.

2. Objectives

The **overall objective** of the study is to evaluate the impact of revised food voucher design features—including voucher amount, food group allocation and enhanced Social and Behavior Change Communication (SBCC)—on household food security, hunger, dietary quality, nutrient intakes and nutrition outcomes among low-income households in the Philippines.

The **specific objectives** of the proposed study are as follows:

To estimate the impact of the revised PHP 3,000 voucher (10:45:45 allocation; continuous redemption) relative to no voucher on:

- Household food expenditure and food acquisition patterns
- Household and individual dietary intake
- Hunger and food insecurity
- Nutrition knowledge

To compare the effects of varying voucher amounts (PHP 3,000 vs. PHP 5,000 vs. PHP 8,000) on:

- Quantity and quality of food purchased and consumed
- Dietary diversity and nutrient adequacy
- Hunger and food insecurity
- Nutrition knowledge

To assess whether higher voucher values (PhP 5,000 and PhP 8,000) generate proportionally larger improvements in dietary quality and nutrition outcomes, particularly among large households with high dependency ratios.

3. Methodology

3.1. Study design

This is a cluster-randomized controlled trial (cRCT) with cross-randomized SBCC enhancement. The REVIVE study includes three main voucher arms: 1) a 3000-peso monthly voucher; 2) a 5000-peso monthly voucher; 3) an 8000-peso monthly voucher; and 4) a control with no voucher. The voucher was accompanied by 6 SBCC sessions, with attendance obligatory for voucher recipients before each redemption. DSWD collaborated with WFP for the development of nutrition education modules, and their implementation was facilitated by local-level trained government staff. The sessions were designed to equip households with critical knowledge about maternal, infant, and household nutrition, and they focused on the use of the Go, Grow, Glow pedagogy, which teaches about carbohydrates, proteins, and fruits and vegetables, respectively. Additionally, sessions cover safe water, sanitation, and hygiene (WASH) practices to foster an environment conducive to better health outcomes and reduced illness.

3.2. Study area

The study is implemented across five provinces—Isabela, Camarines Sur, Manila, Surigao del Norte, and Maguindanao del Norte—with one municipality per province. These were initially selected by DSWD to form a sample of the poor in the country in terms of regional diversity, rural/urban status, and livelihood situation. The sample was split evenly between Manila and the other provinces, so as to be able to understand effects in both highly urbanized and rural settings. Half the study sample is in Tondo, whereas half is in the other 4 regions under more rural conditions. Using global positioning system (GPS) coordinates from the baseline survey, we created a total of 362 clusters, 242 in Tondo and 120 in the other provinces. The minimum size of each cluster was six households outside Tondo and four within Tondo.

Table 1. Sample size for treatment and control groups by locality

Province	Municipality	Control Group	Treatment Arm 1	Treatment Arm 2	Treatment Arm 3	Total Households
			(3000 PHP)	(5000 PHP)	(8000 PHP)	
Isabela	San Mariano	197	228	205	350	980
Camarines Sur	Garchitorena	68	111	87	115	381

Province	Municipality	Control Group	Treatment Arm 1	Treatment Arm 2	Treatment Arm 3	Total Households
			(3000 PHP)	(5000 PHP)	(8000 PHP)	
NCR (Manila)	Tondo I/II	702	748	764	690	2904
Surigao del Norte	Dapa	198	222	164	193	777
Maguindanao	Parang	93	55	67	63	278
Total		1258	1364	1287	1411	5320

Given the common practice of food sharing within communities, the study will also include a spill-over group to assess potential indirect effects of the intervention.

3.3. Study participants

Study participants: The study participants will be drawn from households enrolled in the REVIVE sample (Listahanan 3 eligible households) and residing within the selected study clusters. For the household survey, the primary respondent will be the designated meal planner. For the diet assessment component, eligible households must have at least one woman of reproductive age (15–49 years) with (or without) an index youngest child aged 0–59 months.

Inclusion and exclusion criteria: Inclusion criteria include enrollment in the REVIVE sample, residency in the study cluster, and provision of informed consent. Households will be excluded if a member has a severe illness preventing participation or if informed consent cannot be obtained.

3.4. Sample size

Sample size calculations account for the cluster design of the study and adjust for intra-cluster correlation. The analysis assumes a statistical power of 80% and a significance level (alpha) of 0.05. The study is powered to detect meaningful differences in key outcomes such as food security, hunger, dietary quality and nutrient intakes. This resulted in a sample size of 5320 households in total.

3.5. Study outcomes

The study will collect data on a wide range of nutrition and health outcomes on household meal planner, WRA and their children <5y.

Primary outcomes

- **Nutrition knowledge:** Nutrition knowledge will be assessed through a structured questionnaire administered to the primary caregiver or food preparer in each household. The instrument includes multiple-choice, true/false, and scenario-based items measuring understanding of food groups and their nutritional functions, dietary diversity and balanced meal composition, key micronutrient sources (e.g., iron- and vitamin-rich foods), maternal and child feeding practices, and awareness of the structured voucher allocation rules. Items are aligned with the content of the standard and enhanced SBCC sessions to ensure relevance. A composite nutrition knowledge index will be constructed by summing correct responses and standardizing scores for analysis. Subdomain scores (e.g., dietary diversity knowledge, micronutrient knowledge, child feeding knowledge) will also be generated to assess which dimensions of knowledge were most responsive to the intervention.
- **Energy, macro- and micro-nutrient intake:** These outcomes will be assessed using data collected through 24h dietary recall. Using the dietary intake data, we will estimate the intake of energy, carbohydrate, protein, fat, and eleven micronutrients: vitamin A, thiamin, riboflavin, niacin, vitamin B-6, folate, vitamin B-12, vitamin C, calcium, iron, and zinc. Except for calcium, the probability of adequacy for each micronutrient and each individual in the sample will be calculated through the probability approach. Probabilities will be averaged across the 11 micronutrients to calculate the mean probability of adequacy, a summary indicator of diet quality.
- **Healthiness of the diet:** We will describe the individual diet through consumption of specific food groups, considered healthy and unhealthy. A 24h recall will be used to assess intake of fruits and vegetables, sweet and sugared beverages, ultra-processed foods, and fried snack foods consumption, among others. Intake will be assessed in terms of frequency and quantity (g), number of servings per day, and contribution to overall energy intake. The healthiness of the diet of WRA and children under 5y will be assessed as follows: (1) percentage consuming the ten food groups as defined by the Minimum Dietary Diversity for Women; (2) the Global Dietary Quality Score – GDQS. The GDQS has two subdimensions: the nutrient adequacy subdimension and the NCD risk subdimension. Weights to calculate the score are based on the quantity consumed. The GDQS has been validated for use in nonpregnant and nonlactating women. In addition, we will calculate the Global Diet Recommendation (GDR) score which will be based on data collected through the Diet Quality-Questionnaire (DQQ). Infant and young child feeding practice indicators will also be estimated for children under 5 years.

Secondary outcomes

- **Household Food Consumption Score (FCS)** is used to assess household dietary quality and food consumption patterns over a seven-day recall period. The FCS is a composite indicator that integrates three dimensions of food consumption—dietary diversity, frequency of consumption, and the nutritional value of different food groups.

During the survey, respondents report how many days in the past seven they consumed items from the standardized food groups. Each food group's reported frequency (capped at a maximum of seven days) is multiplied by a pre-assigned weight reflecting its relative nutritional importance. The weighted scores for all food groups will be then summed to generate the household's overall FCS.

- **Hunger and food insecurity:** Food insecurity and hunger were measured using a structured household questionnaire covering experiences over the previous four weeks, adapted from internationally validated food insecurity experience scales. Respondents were asked whether, due to lack of money or other resources, their household: (i) worried about not having enough food; (ii) was unable to eat healthy and nutritious food; (iii) ate only a limited variety of foods; (iv) skipped meals; (v) ate less than they felt they should; (vi) ran out of food; (vii) went to sleep hungry; or (viii) went a whole day and night without eating. For each occurrence-based question, respondents were further asked about the frequency of the experience during the recall period. These items capture increasing severity of food insecurity, from anxiety about food access to extreme deprivation, and were used to construct categorical indicators of food insecurity severity as well as continuous indices for impact analysis.
- **Nutritional and health outcomes:** For children, we will calculate the height-for-age z-scores (HAZ), weight-for-age z-scores (WAZ) and weight-for-height z-scores (WHZ) using the WHO growth standard. We will use the WHO cut-offs to interpret children's body weight, i.e., underweight, stunting, wasting. For WRA, BMI will be used as one of the markers of nutritional status. BMI will be calculated as $\text{weight}/\text{height}^2$. We will use the WHO cut-offs, i.e., underweight as BMI < 18.5, overweight as BMI 25.0 to 29.9, and obese as BMI ≥ 30.0 . We will also use the cut-offs for Asian populations.

Child health outcomes were assessed using a two-week recall period, during which the primary caregiver reported whether each eligible household member experienced any of the following symptoms: fever, cough/cold, fast or short breathing, diarrhea, fatigue, nausea or vomiting, serious underweight, or a diagnosed micronutrient deficiency (e.g., vitamin A and/or iron deficiency).

- **Household Food and Non-Food Expenditures**
 - **Food expenditure** will be collected using a four-week recall period. Respondents are asked to report the total value of all food consumed by the household during the past four weeks, including food purchased in cash or on credit, received as gifts or transfers, obtained from own production, and redeemed through the Walang Gutom food voucher. The module cover food consumed by all household members and non-members who regularly shared meals with the household (defined as individuals consuming at least eight lunches or dinners during the reference period; breakfast and snacks were excluded). Food expenditure estimates therefore reflect total household food consumption, regardless of source.
 - **Non-food expenditures** will be collected using a six-month recall period to estimate average monthly spending. Respondents report typical monthly expenditures (in Philippine pesos) across major categories, including education, health care, utilities (electricity and water), rent (actual or imputed), fuel (including LPG), transportation, transfers and gifts, social events (festivals, funerals, weddings), communication expenses (internet and mobile load), personal hygiene products, leisure and entertainment, gambling, clothing and toys, alcohol, tobacco, durable goods and furniture, debt payments, and other miscellaneous expenses not captured elsewhere.

Reported six-month expenditures will be averaged to generate standardized monthly non-food expenditure measures.

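### The primary nutrition knowledge index scores awareness of the voucher's own allocation rules, which biases voucher-versus-control differences upward

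*Protocol*

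**What the plan says.** Section 3.5 of the protocol lists nutrition knowledge first among the primary outcomes. The questionnaire is "administered to the primary caregiver or food preparer in each household", so control households answer it too. Its content includes "maternal and child feeding practices, and awareness of the structured voucher allocation rules". On scoring, the section states: "A composite nutrition knowledge index will be constructed by summing correct responses and standardizing scores for analysis". It excludes no item from that sum. Subdomain scores are to be produced as well; the examples given are dietary diversity, micronutrients and child feeding.

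Section 3.1 defines the comparator as "4) a control with no voucher" and ties the education sessions to the voucher: "The voucher was accompanied by 6 SBCC sessions, with attendance obligatory for voucher recipients before each redemption". Section 2 makes nutrition knowledge one of the outcomes of its first specific objective: "To estimate the impact of the revised PHP 3,000 voucher (10:45:45 allocation; continuous redemption) relative to no voucher on".

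**The concern.** The 10:45:45 split is a spending rule of this programme, changed from the 50/30/20 split of the first pilot. It is not a fact about nutrition. A control caregiver who knows food groups, micronutrient sources and child feeding perfectly has no voucher through which to learn it. A voucher household meets it at redemption, even if the sessions taught nothing about nutrition. Items on the rule therefore measure exposure to treatment, yet they count as nutrition knowledge.

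At stake is one of the three primary outcome groups, in the comparison with no voucher. A difference could be reported as a gain in nutrition knowledge when part or all of it reflects familiarity with how the voucher works.

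**Working it through.** **What the text settles.** Three statements have to be read together. The instrument contains rule items, and the composite sums all correct answers (section 3.5). The instrument goes to every household (section 3.5). The objective compares voucher with no voucher (sections 2 and 3.1). If the nutrition items show no effect, the expected difference in the composite equals the difference on the rule items alone. That difference is positive whenever voucher households know the rules better than controls do.

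**The plan's own figures.** The Table 1 arm totals add up: 1,258 + 1,364 + 1,287 + 1,411 = 5,320. The total cannot be rebuilt from a power formula, because section 3.4 gives alpha 0.05 and 80% power but no effect size, SD or ICC.

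**Minimum detectable difference, control (1,258) against 3,000 pesos (1,364).** The ICCs are assumptions, and the test is taken as two-sided.

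- Mean cluster size: 5,320 / 362 = 14.7.
- Design effect: 1 + (14.7 − 1) × ICC = 1.27, 1.68 and 2.37 for ICC 0.02, 0.05 and 0.10.
- Detectable difference: (1.96 + 0.84) × √[design effect × (1/1,258 + 1/1,364)] = 0.124, 0.142 and 0.169 SD.

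This uses the mean cluster size only. Clusters average 12.0 households in Tondo (2,904 / 242) and 20.1 elsewhere (2,416 / 120).

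**Artefact with no true effect on any nutrition item.** For k rule items, d = k × (p_voucher − p_control) / SD of the sum score. The variance of the sum is Σs² + r × [(Σs)² − Σs²], where s = √[p(1 − p)] for each item and r is the inter-item correlation. Assumptions: 20 or 30 items; 1 to 3 rule items; 60% correct on the nutrition items; rule items 10–25% correct in control and 50–80% in voucher households; r = 0.05 or 0.15.

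For 20 items, 2 of them rule items, 25% against 80% correct, and r = 0.05:

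- Σs² = 18 × 0.24 + 2 × 0.1875 = 4.695.
- Σs = 18 × 0.490 + 2 × 0.433 = 9.684.
- Variance = 4.695 + 0.05 × (93.78 − 4.695) = 9.15, so SD = 3.02.
- d = 2 × 0.55 / 3.02 = 0.36.

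| Items | Rule items | Correct, control / voucher | r | Score SD | d | Chance of p < 0.05, ICC 0.10 to 0.02 |
|---|---|---|---|---|---|---|
| 30 | 1 | 25% / 50% | 0.15 | 6.18 | 0.04 | 10–15% |
| 20 | 1 | 25% / 80% | 0.15 | 4.27 | 0.13 | 57–83% |
| 20 | 1 | 25% / 80% | 0.05 | 3.04 | 0.18 | 85–98% |
| 20 | 2 | 25% / 80% | 0.15 | 4.25 | 0.26 | 99% or more |
| 20 | 2 | 25% / 80% | 0.05 | 3.02 | 0.36 | above 99% |
| 20 | 3 | 10% / 80% | 0.05 | 2.90 | 0.72 | above 99% |

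The first and last rows are the extremes of the assumed range. With the rule items left out, the artefact is zero by definition and the false-positive rate returns to 5%.

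**The case against.** **Size.** Every input to the artefact is assumed. In the mildest case it is 0.04 SD, well below what the trial could detect. Section 3.4 does not name nutrition knowledge among its examples of outcomes the study is powered for, so the detectable difference is a benchmark calculated here, not the protocol's. This stands: the direction is known, the size is not.

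**Controls may know the rules.** The protocol never says that controls get no sessions; that is inferred from section 3.1. Section 3.2 expects food sharing and plans a spill-over group, and sections 3.5 and 3.6 record Walang Gutom vouchers and participation. This could narrow the gap. Nothing suggests that controls would know the rules as well as households that redeem under them.

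**The effect is positive by construction.** A reader might infer this, but the documents do not support it. The sign of the whole composite also depends on the nutrition items, whose effects are unknown. Only the upward bias follows from the text.

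**A gain would be credited to the SBCC sessions.** A reader might infer this too. Section 3.1 bundles sessions with the voucher, so voucher against control cannot isolate the sessions whichever items are scored. The SBCC enhancement is cross-randomised. If that contrast lies among voucher holders, both sides face the same rules and the artefact largely cancels.

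**The subdomain scores protect the reader.** In part they do: an effect confined to rule items would appear in the composite without matching subdomain effects. But these scores supplement the primary composite and do not replace it.

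**Alignment with the sessions is intended.** The protocol says: "Items are aligned with the content of the standard and enhanced SBCC sessions to ensure relevance". That is reasonable for nutrition facts, which a control respondent can learn elsewhere. It does not make a programme spending rule nutrition knowledge.

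**Item lists belong in the SAP.** A final scoring key may. Here the protocol itself puts the rule items in the instrument and defines the index as the sum, so the defect is in the stated definition.

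**Conclusion.** The point holds for comparisons of a voucher arm with control. As defined, the primary knowledge index counts awareness of the voucher rules, and the difference from control is biased upward even if nutrition knowledge is unchanged. This rests on voucher households knowing the rules better than controls, which follows from who redeems. Knowledge among controls may shrink the bias but is unlikely to remove it. Comparisons among 3,000, 5,000 and 8,000 pesos are largely unaffected, because all three arms face the same rules.

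The protocol does not allow the size to be fixed. Over the assumed range it is about 0.04 to 0.72 SD, against a detectable difference of about 0.12 to 0.17 SD. One rule item in 20, answered correctly by 25% of controls and 80% of voucher households, already gives 0.13 to 0.18 SD, about the size of the detectable difference.

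**What to change.** Define the primary composite from the nutrition items only: food groups and their functions, dietary diversity and balance, micronutrient sources, and maternal and child feeding. Keep the allocation-rule items in the questionnaire, but report them separately as a measure of programme awareness or implementation.

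This takes one sentence in the index definition in section 3.5. It needs no new data and no change to the questionnaire. The reported knowledge effect against control may be smaller. Standardising the score to the control mean and SD would be a reasonable choice, but it is optional and not part of this error.

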- **24-hour dietary recall:** We will record food consumption for WRA and children under 5y through a quantitative 24-h recall administered by a trained surveyor. A second quantitative 24h recall will be conducted on 20% subsample, on 2 nonconsecutive weekdays within 1 or 2 weeks for the same mothers/children. The 24-h recall interview technique will be adapted from the multiple-pass method: 1) a list of meals, dishes, and all food items and beverages consumed will first be recorded and their place of preparation (at home or outside) will be noted; 2) interviewees will be asked for a full description of ingredients in all mixed dishes; 3) the method of preparation will be noted (e.g. time of cooking, whether the cooking receptacle is covered); 4) amounts (using household measures, direct weighing, or food models as appropriate) will be assessed separately for each ingredient and the portions eaten; 5) waste and non-consumed parts will be estimated; and 6) interviewees will systematically be prompted for specific foods of interest to the study, such as snacks and drinks. We will also collect data on where each food consumed was obtained. Catalogs of standard recipes will be created, one for dishes prepared and consumed at home and one for dishes consumed outside the home (data to be collected among restaurants and other food outlets, including street-food vendors). Finally, an algorithm will be developed to ensure that all days of the week are properly represented in the sample.
- **Anthropometric measurement:** Anthropometric data (height and weight) will be measured directly by trained field staff using standardized equipment and procedures. Measurements will follow internationally recognized protocols to ensure quality and comparability.

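### The GDQS is a primary outcome in groups beyond its stated validation, and child nutrient adequacy is computed from birth with no described provision for breast milk

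*Protocol*

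**What the plan says.** Protocol section 3.5 lists the healthiness of the diet among the primary outcomes. It sets the population and the measures together: "The healthiness of the diet of WRA and children under 5y will be assessed as follows". The second listed measure is "2) the Global Dietary Quality Score". Later in the same paragraph comes the only statement on validity: "The GDQS has been validated for use in nonpregnant and nonlactating women". Infant and young child feeding (IYCF) indicators are planned for children in addition to the GDQS, not in its place.

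Section 3.3 makes a household eligible for the diet component if it has "at least one woman of reproductive age (15–49 years) with (or without) an index youngest child aged 0–59 months". The exclusions are few: "Households will be excluded if a member has a severe illness preventing participation or if informed consent cannot be obtained". Pregnancy and lactation are not mentioned there.

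For nutrients, also a primary outcome, section 3.5 says that, except for calcium, "the probability of adequacy for each micronutrient and each individual in the sample will be calculated through the probability approach". The source is the 24-hour recall. Section 3.6 on data collection defines who receives it: "We will record food consumption for WRA and children under 5y through a quantitative 24-h recall administered by a trained surveyor". That recall lists meals, dishes, foods and drinks, and quantifies them by household measures, weighing or food models. Breast milk is not mentioned anywhere in the protocol.

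**The concern.** There are two separate problems of population.

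First, the GDQS is assigned to a wider group than the one in which the protocol says it has been validated. A result in children, or in a mixed group of women, would then be reported as a primary finding on a scale whose meaning in those people the protocol does not support.

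Second, for a breastfed child, recalled foods and beverages are only part of intake. If nothing is added for breast milk, recorded energy, nutrients and adequacy fall below true values, and the shortfall depends on feeding mode. Feeding mode may respond to the intervention: section 3.1 says the SBCC sessions cover infant nutrition and that voucher recipients must attend them. More breastfeeding in a voucher arm would then look like poorer child intake, and earlier weaning would look like better intake.

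**Working it through.** The protocol gives no figure for this point, so there is none to reproduce. The check is mainly a comparison of texts.

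**Step 1. GDQS: validated group against target group.**

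| Group | Within the stated validation (3.5) | Assigned the GDQS (3.5) | Excluded (3.3) |
|---|---|---|---|
| Nonpregnant, nonlactating women | yes | yes | no |
| Pregnant women aged 15–49 | no | yes | no |
| Lactating women aged 15–49 | no | yes | no |
| Children under 5 | no | yes | no |

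Three of the four groups lie outside the stated validation, and nothing in the protocol restricts or separates them.

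**Step 2. Nutrients: population against instrument.** Adequacy is computed for every individual (3.5). The recall covers all children under five (3.6), and the index child may be aged "0" months upward under the eligibility rule (3.3). No step of the recall describes how breast milk is recorded, quantified or assumed.

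**Step 3. How this enters an arm comparison.** Let p be the share of children breastfed in an arm and b their mean intake from breast milk. If only recalled foods and beverages count:

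- recorded mean = true mean − p × b
- recorded difference (voucher − control) = true difference − (p_v × b_v − p_c × b_c)

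If p × b is the same in both arms, the term cancels for mean energy or nutrient intake. Levels are then too low, but the difference is not shifted. If p or b differs by arm, the difference is shifted by that amount. The probability of adequacy is not linear in intake, so even an equal loss can change the size of its contrast. The protocol gives no value for p or b, so no figure can be put on the shift.

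**Step 4. Size of the exposed age groups.** The protocol reports no child ages. Assuming ages uniform over 60 months (0–59):

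- under 6 months: 6/60 = 10%
- under 12 months: 12/60 = 20%
- under 24 months: 24/60 = 40%

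Because the index child is the youngest, the true shares may be higher. These are shares by age, not shares breastfed.

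**The case against.** **The protocol does not say the GDQS fails elsewhere.** This is correct. A reader might infer that the score is invalid in children and in pregnant or lactating women, but the sentence only reports where it has been validated. What stands is that the protocol gives no support for its use in the added groups while making it primary there.

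**The breast-milk point rests on silence.** An assumed intake by age could sit in an SAP or dietary manual that is not shown. A reader might infer that breast milk is definitely left out and that exclusively breastfed infants will be recorded with almost no intake. The documents do not establish that, so the point is conditional. It survives because the protocol does fix the population as every individual, from birth, and an analysis plan that narrowed this would depart from it.

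**Randomization protects the comparison.** In part it does. A shortfall common to all arms mainly lowers levels and adds noise. A false difference in mean intake needs treatment to change breastfeeding or weaning. The documents give no evidence that it will, only a plausible route through the SBCC content.

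**Restricting the women's primary analysis to the validated group would do harm.** This is right. Pregnancy and lactation at the time of recall are observed after assignment, so conditioning on them would select on something treatment could affect. The same reasoning favours age over breastfeeding status for children.

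**Other diet measures are planned.** The IYCF indicators and the DQQ-based score do mean that the GDQS is not the only measure. They do not narrow the population assigned to it.

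A reader might also extend the point to the ten food groups in women, or to BMI in pregnancy. The validity sentence concerns the GDQS alone and does not support either extension.

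**Conclusion.** The point holds in two parts of different strength.

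The GDQS part follows from the protocol's own words: the score is assigned, as a primary outcome, to children and to pregnant and lactating women, in whom by that statement it is not shown valid. How many such women will be enrolled is unknown. It would be tempting to say that lactating women are common in the sample, but the eligibility rule admits women with or without a young child and gives no counts.

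The breast-milk part is conditional. If only recalled foods and beverages count, intake and adequacy in breastfed children are understated, and any arm difference in breastfeeding or weaning would appear as a difference in intake. The 40% and 10% rest on an assumed uniform age distribution; they indicate which age groups are exposed and do not measure bias. Both parts should be corrected in the protocol, because the protocol is what fixes these populations.

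**What to change.** 1. **Children, GDQS.** Remove it as a primary outcome for children. Rely on the IYCF indicators already planned, at the ages they cover.
2. **Children, energy, nutrients and adequacy.** Make children aged 24 months or more at recall the main population. Define it by age, because breastfeeding may respond to treatment. Report 6–23 months as intake from complementary foods only and leave out 0–5 months, unless a stated breast-milk intake assumption is applied.
3. **Women, GDQS.** Keep the full randomized comparison of WRA. Record pregnancy and lactation status, show it by arm, and report the GDQS in nonpregnant, nonlactating women alongside. Do not make the primary analysis conditional on lactation.

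The cost is a change to the outcome wording, one or two added questions, and fewer children in the main child analysis. Under the uniform-age assumption about 60% of children (36/60) would remain in it. The loss could be larger because the index child is the youngest, so precision for the child outcomes should be rechecked once ages are known.
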